5.1.6 Unblinding

5.1.6.1 Unblinding for final analyses

Full randomization information will be made available for data analysis only after database closure in accordance with Actelion standard operating procedures (SOPs).

5.1.6.2 Unblinding for IDMC

A SAC, not otherwise involved in the design, conduct and analysis of the study, will have access to the randomization code in order to prepare unblinded reports for review by the IDMC (for IDMC review meetings during the course of the trial). The randomization code will be made available to the SAC in accordance with the sponsor's SOPs.

5.1.6.3 Unblinding for suspected unexpected serious adverse reactions

When a suspected unexpected serious adverse reaction (SUSAR) occurs for a subject participating in the study, Actelion Global Drug Safety will request the unblinding of the treatment assignment. The randomization code will not be communicated to the site staff or to the Actelion study team; unblinded SUSAR information will be anonymized and provided to Actelion Global Drug Safety, respective health authorities and Institutional Review Boards (IRBs) / Independent Ethics Committees (IECs) only. SUSARs will be reported to investigators in a blinded fashion.

5.1.6.4 Emergency procedure for unblinding

The investigator, study staff and sponsor staff must remain blinded to the subject's treatment assignment. The identity of the study treatment may be revealed only if the subject experiences a medical event, the management of which would require knowledge of the blinded treatment assignment. In this case, the investigator can receive the unblinded randomization code for study treatment allocation through the IRT. In these situations, the decision to unblind resides solely with the investigator. Whenever it is possible and if it does not interfere with (or does not delay) any decision in the best interest of the subject, the investigator is invited to discuss the intended code break with Actelion.

5 December 2018, page 94/376

The occurrence of any code break during the study must be clearly justified and explained by the investigator. The investigator must not disclose the unblinded treatment in the eCRF or to the sponsor or its delegates. In all cases, Actelion must be informed as soon as possible before or after the code break.

The circumstances leading to the code break must be documented in the site study file and eCRF.

Refer to the IRT guidelines for complete information regarding the IRT procedures for randomization, study drug assignment, and unblinding.

5.1.7 Study treatment supply

Manufacture, labeling, packaging and supply of study treatments will be conducted according to Good Manufacturing Practice, Good Clinical Practice (GCP) and any local or national regulatory requirements.

All treatment supplies are to be used only in accordance with this protocol and not for any other purpose.

5.1.7.1 Study treatment packaging and labeling

5.1.7.1.1 Study treatment packaging

Study treatment is provided as capsules and tablets and supplied in childproof blister packs.

5.1.7.1.2 Study treatment labeling

Study treatment is labeled to comply with the applicable laws and regulations of the countries in which the study sites are located.

5.1.7.2 Study treatment distribution and storage

Treatment supplies must be kept in an appropriate, secure area and stored according to the conditions specified on the medication labels. The study drug must be stored below 25 °C. The study drug must not be refrigerated.

5.1.7.3 Study treatment dispensing

The subjects will receive sufficient study treatment to cover the period up to the next scheduled visit. Alternatively, scheduled study medication dispensing/return procedures may be adapted according to the site practice (i.e., if the subject comes to the investigational site more frequently than the scheduled visits, it is then possible to dispense medication in smaller quantity). Subjects are asked to return all used, partially used and unused study treatment blister packs at each visit. If the subject forgets to bring the remaining study treatment to a study visit, she/he must be instructed not to take any tablet/capsules from the remaining study treatment and to bring it at the next visit.

Ponesimod / ACT-128800 Relapsing multiple sclerosis Protocol AC-058B301, OPTIMUM Version 7 5 December 2018, page 95/376

Confidential

An accurate record of the date and amount of study treatment dispensed to each subject must be available for inspection at any time.

5.1.7.4 Study treatment return and destruction

On an ongoing basis and/or on termination of the study, the monitor will collect used and unused subject kits, which will be sent to the warehouse, where Actelion or a deputy will check treatment reconciliation.

5.1.8 Drug accountability and compliance

5.1.8.1 Drug accountability

Records of study drug dispensed and returned, dosages administered, and intervals between visits are kept during the study. Study treatment accountability must be performed by the study staff on the day of the visit and before providing further study treatment, in order to ensure that the subject is compliant with study requirements. Study treatment accountability is checked by the monitor during site visits and at EOS.

5.1.8.2 Drug compliance

Subjects' compliance with study drug intake will be recorded using an electronic diary. On each day, the subjects will be asked to enter the date, time, number of capsules (and tablets, if applicable) taken, and the unique blister-card identifying number from which the capsules (and tablets, if applicable) are (were) taken from. In addition, during the up-titration, the position of the well on the blister card will be recorded in order to check that capsules and tablets (if applicable) were taken in the correct sequence [see gradual up-titration in Section 5.1.3.1].

The electronic diary will give feed-back and instruct the subject to contact the investigator as soon as possible before taking next dose, whenever one of the following is observed:

- Dose is taken in an incorrect sequence during the up-titration (e.g., capsule at position 6 taken before capsule at position 4 on the blister card);
- 1 or more dose(s) (capsule and/or tablet if applicable) are missed during the up-titration;
- 4 or more doses are missed during the maintenance.

Additionally, feedback will be given to the subject whenever 1 to 3 dose(s) are missed during the maintenance.

At each visit, the site personnel will crosscheck the subject's compliance as indicated in the electronic diary against the study drug accountability [see Section 5.1.8.1]. Subjects will be asked to explain the observed discrepancies. Interruptions with known dates will be recorded accordingly in the study drug log [see Section 5.1.9]. Study drug intake requirements will be re-explained to the subject each time an interruption is observed.

5.1.9 Study treatment dose adjustments and interruptions

Study drug up-titration, other than described in Section 5.1.3, is prohibited. Study drug down-titration is not foreseen in any situation and is prohibited.

Study drug interruption should be avoided. If study treatment intake is interrupted by the subject for any reason, she/he must immediately inform the investigator/treating neurologist.

Study treatment may be temporarily interrupted in response to an AE, a diagnostic or therapeutic procedure, a laboratory abnormality, or for administrative reasons. Study-specific criteria for interruption of study treatment are described in Section 5.1.13. The duration of an interruption is determined by the investigator and is not limited in time. At maximum, it will last until the investigator deems the subject necessary to require another MS treatment. In this event, it is recommended performing an accelerated elimination procedure [see Section 5.1.14] before a new immunomodulatory treatment for MS is started.

Detailed guidance on how to re-initiate study drug in the event of drug interruption is provided in Section 5.1.10.

Study treatment dose adjustments/interruptions must be recorded in the eCRF.

5.1.10 Guidance for re-initiation of study treatment in the event of study treatment interruption

If study drug intake is interrupted by the subject for any reason, she/he must immediately inform the principal investigator / treating neurologist.

The following guidance is provided for re-initiation of investigational study drug after study drug interruptions.

A schematic overview of the re-initiation algorithm is given below in Figure 5.

Depending on the day, time, and duration of study drug interruption, the following procedures will be followed.

- If the subject missed taking the dose in the morning:
 - The dose should be taken at any time on the same day.
 - Regular dosing should be continued with the morning dose on the following day.
- If the subject missed taking the dose for one or more days during treatment up-titration (from 1 to 14 days after the first-dose of initiation/re-initiation of the study drug):

5 December 2018, page 97/376

- The original up-titration scheme needs to be re-applied, with the initial dose and gradual up-titration steps for 14 days after the first-dose of re-initiation of the study drug.
- On the day of the re-initiation of investigational study drug, the subject must be monitored for at least 4 h post-dose by the first-dose administrator, following the cardiac assessment schedule and applying the discharge criteria as described for Day 1 [see Section 5.1.11].
- If the subject missed taking the dose for up to three consecutive days during treatment maintenance (from 14 days after the first dose of initiation/re-initiation of the study drug onwards):
 - Dosing should be continued in the morning following the last day without investigational study drug intake, with the same dose taken prior to study drug interruption.
 - Study drug intake may be re-initiated by the subject at home.
 - Subjects must be instructed to contact the investigator immediately if they experience any symptoms of bradycardia (e.g., dizziness, vertigo, syncope).
- If the subject missed taking the dose for four or more consecutive days during treatment maintenance (from 14 days after the first dose of initiation/re-initiation of the study drug onwards):
 - The original up-titration scheme for the investigational study drug needs to be re-applied.
 - On the day of the re-initiation of treatment, the subject must be monitored for at least 4 h post-dose by the first-dose administrator, following the cardiac assessment schedule and applying the discharge criteria as described for Day 1 [see Section 5.1.11].

Whenever the investigator / treating neurologist becomes aware that the subject did not report having missed the study drug intake for one or more days during up-titration or four or more days during maintenance and has continued dosing, the subject should be interviewed by the investigator / treating neurologist for any symptoms related to bradycardia and further examinations (e.g., 12-lead ECG, BP measurement) may be performed at the discretion of the investigator / treating neurologist. Based on an assessment of the clinical findings and the likelihood of subject's adherence to treatment, the investigator / treating neurologist will determine whether the subject can continue regular dosing, need to re-initiate treatment, or should permanently discontinue treatment.

Ponesimod / ACT-128800 Relapsing multiple sclerosis Protocol AC-058B301, OPTIMUM Version 7 5 December 2018, page 98/376

Confidential

5.1.11 Criteria for discharge from cardiac monitoring on Day 1, and on the first day of re-initiation of the investigational study drug following treatment interruptions

At the time of discharge from cardiac monitoring (i.e., when the evaluation of the pre-dose and all the hourly post-dose ECGs until 4 h post-dose have been obtained) on Day 1, and on the first day of re-initiation of study drug following drug interruptions, the following criteria must be met:

- ECG-derived resting HR > 45 bpm, and if HR < 50 bpm it must not be the lowest value post-dose;
- SBP > 90 mmHg;
- QTcF < 500 ms and QTcF increase from pre-dose < 60ms;

• No persisting significant ECG abnormality (e.g., AV block second- or third-degree) or ongoing AE requiring continued cardiac monitoring or prohibiting study continuation as an out-patient.

If the subject does not meet the discharge criteria (as described above) at 4 h post-dose, the subject should be carefully monitored for an additional period, and a 12-lead ECG and a BP measurement must be performed every hour. The subject can be discharged from cardiac monitoring as soon as the above criteria are met.

Should the subject not meet the criteria for discharge from cardiac monitoring at 12 h postdose, she/he must be permanently discontinued from study drug. Subjects who are permanently discontinued should not be discharged from cardiac monitoring before vital signs return to near baseline values or until there is no persisting ECG abnormality (e.g., AV block second degree or higher), ongoing AE requiring continued cardiac monitoring, or until medically indicated.

5.1.12 Premature discontinuation of study treatment

In the study, the premature discontinuation of study treatment is defined as a permanent discontinuation of study treatment earlier than the planned treatment duration of 108 weeks. The decision to prematurely discontinue study treatment may be made by the subject, the investigator or Actelion.

A subject has the right to prematurely discontinue study treatment at any time by withdrawal from treatment only or by withdrawal from treatment and any further participation in the study.

The investigator should discontinue study treatment for a given subject if, on balance, she/he believes that continued administration would be contrary to the best interests of the subject. In case of clinically significant progression of the disease as judged by the investigator, the investigator should consider switching to another potentially more effective therapy, discuss alternative treatment options with the subject, and document the outcome of this discussion in the medical records.

Premature discontinuation of study treatment may also result from a decision by Actelion, e.g., in case of premature termination or suspension of the study [see Section 9.3].

The main reason and whether discontinuation of study treatment is the decision of the subject, the investigator, or Actelion must be documented in the eCRF.

A subject who prematurely discontinues study treatment is NOT considered as withdrawn from the study and will be followed up until Week 108 in the PTOP or until the end of the safety FU period (30 days after study drug discontinuation), whichever comes last [see

Section 3.1.3], provided that the subject's consent for this limited participation in the study has not been withdrawn.

A subject who prematurely discontinues study treatment and withdraws consent to participate in any further study assessments is considered withdrawn from the study. Subjects who die or are lost to FU are also considered as withdrawn from the study. Withdrawal from the study and FU medical care of subjects withdrawn from the study is described in Sections 9.2 and 9.4, respectively.

In the event of permanent discontinuation from study drug due to any reason, the investigator should consider prescribing appropriate treatment for MS according to the local clinical practice and availability. The investigator should exercise caution when considering the switch to another immunomodulatory MS treatment. Initiation of immunomodulatory therapies is best avoided during the FU period of 15 days and until an accelerated elimination procedure for teriflunomide has been conducted to minimize the risk of immunosuppression.

5.1.13 Study-specific criteria for interruption / premature discontinuation of study treatment and management of clinically relevant events

An accelerated elimination procedure must be used by all subjects permanently discontinued, after the last dose of study drug [see Section 5.1.14].

5.1.13.1 Cardiovascular

Subjects **must** be permanently discontinued from study drug if:

- The following change in HR is observed at any time throughout the study, as documented by 12-lead ECG:
 - HR < 30 bpm, or
 - HR < 40 bpm is sustained for at least 1 h and is associated with symptoms of bradycardia (e.g., syncope, dizziness, or vertigo), or
- QTcF > 500 ms is observed at any time throughout the study, as documented by 12-lead ECG, or
- The subject does not meet the criteria for discharge from cardiac monitoring on Day 1, or on the first day of re-initiation of study drug following drug interruptions after 12 h post-dose monitoring, or
- The subject needs to receive systemic chronic treatment with β -blockers, diltiazem, verapamil, digoxin, or any other anti-arrhythmic or HR lowering therapy [non-exhaustive list of drugs provided in Appendix 4].

FU monitoring will have to be provided until the event resolves, the condition is stable, or the change is regarded as no longer clinically relevant.

Continuous ECG monitoring is recommended for subjects who meet study drug discontinuation criteria related to bradycardia or other arrhythmia. Subjects who are permanently discontinued should not be discharged from the monitored setting before vital signs return to near baseline values and until there is no persisting ECG abnormality (e.g., QT prolongation, AV block second degree or higher) or ongoing AE requiring (continued) cardiac monitoring, or until medically indicated. Any clinically relevant finding meeting the definition of an AE will be recorded accordingly in the respective eCRF.

In case of any signs and symptoms of bradycardia or other arrhythmia (e.g., syncope, palpitations, etc.), at any time during the study treatment, the first-dose administrator and/or a cardiologist may be consulted. In case a cardiac origin is suspected, permanent discontinuation of study drug should be considered.

In case subjects experience sustained *de novo* or worsening of pre-existing hypertension during the course of the treatment with the study drug which, in the opinion of the investigator, cannot be adequately controlled by medications, study drug should be permanently discontinued.

5.1.13.2 Hematological abnormalities and infections

Subjects **must** be permanently discontinued from study drug at any time throughout the study in the event of:

- Confirmed neutrophil count $< 1.0 \times 10^{9}/L (< 1000 \text{ cells/mm}^{3})$
- Confirmed platelet count $< 50 \times 10^9$ /L ($< 50\ 000\ cells/mm^3$)
- Confirmed total lymphocyte count $< 0.2 \times 10^9/L$ ($< 200 \text{ cells/mm}^3$)

Confirmation will be done as follows:

Whenever a neutrophil count $< 1.0 \times 10^{9}$ /L, a platelet count $< 50 \times 10^{9}$ /L, or a total lymphocyte count $< 0.2 \times 10^{9}$ /L, is recorded by the central laboratory, an alert will be sent to the principal investigator and the sponsor. The principal investigator will immediately contact the subject and ask her/him to return to the site within 48 h at the latest to repeat the test at trough level (pre-dose) by the central laboratory (unless the clinical situation mandates immediate local testing). If the repeat test confirms a neutrophil count $< 1.0 \times 10^{9}$ /L, a platelet count $< 50 \times 10^{9}$ /L, or a total lymphocyte count $< 0.2 \times 10^{9}$ /L the study drug must be discontinued. Neutrophil, platelet, or lymphocyte counts must be monitored at least once a week by the central laboratory until the neutrophils or platelets have returned to $\ge 80\%$ of the baseline value or the lymphocyte count has returned to

EudraCT 2012-000540-10 Doc No D-18.388

Confidential

 $\geq 0.8 \times 10^{9}$ /L or $\geq 80\%$ of the baseline value. Any clinically relevant finding meeting the definition of an AE will be recorded accordingly in the eCRF.

In the event of a decrease of neutrophil or platelet not reaching the above alert levels, test at trough level (pre-dose) may be repeated. Upon confirmation of the decline over time of neutrophil or platelet counts, study drug may be interrupted at the discretion of the investigator. Possible causes for this decline including signs and symptoms suggestive of an infection should be assessed.

In the event of a suspected opportunistic infection of the CNS, the study drug must be interrupted and the subject referred to an expert in infectious diseases for further examination and treatment. For any other infection the subject should be treated as clinically indicated and study drug may be interrupted or permanently discontinued at the discretion of the investigator. In case of study drug interruption the subject will be closely observed and if the infection is resolved or not confirmed and the benefit/risk balance is considered acceptable for the subject to resume study treatment, the study drug may be re-initiated at the discretion of the investigator.

In the event of permanent discontinuation from study drug due to infection, adequate treatment needs to be provided and the subject must be monitored until complete resolution of the infection.

A guidance for screening and monitoring of subjects for opportunistic infection is provided in Sections 5.1.13.2.1 and 5.1.13.2.2. Subjects must be advised to be proactive and alert in reporting any unusual neurological symptom and any signs and symptoms indicative of systemic infections, such as fever, malaise and fatigue.

In the event of a suspected opportunistic infection in the CNS, unscheduled brain MRI scans may be performed at the investigator's request.

5.1.13.2.1 Guidance for screening, exclusion and on-treatment monitoring of subjects for progressive multifocal leukoencephalopathy

Progressive multifocal leukoencephalopathy (PML) is an opportunistic infection of the CNS that can lead to death or severe disability. Active replication of the human polyoma John Cunningham Virus (JCV) in glial cells of the brain, causing lytic death in oligodendrocytes, is the underlying pathobiology of PML. The infection typically arises in severely immunocompromised subjects e.g., those with HIV infection, malignant disease, or transplanted organs. Development of PML is extremely rare in immunocompetent individuals. People with autoimmune rheumatic diseases, especially systemic lupus erythematosus, are also at higher risk of PML [Kappos 2011].

MS subjects treated with natalizumab are at increased risk of developing PML. In addition to natalizumab, cases of PML have been reported in subjects treated with various drugs,

usually in combination with corticosteroids, including alkylating agents (e.g., cyclophosphamide, carmustine, and dacarbazine), purine analogues (e.g., fludarabine, cladribine, and azathioprine), immunosuppressants (e.g., cyclosporine, tacrolimus, sirolimus, and mycophenolate), and therapeutic monoclonal antibodies (e.g., rituximab, infliximab, etanercept, basiliximab, daclizumab, efalizumab, alemtuzumab, and muromonab-CD3) [Kappos 2011].

Clinical features indicative of PML are:

- Subacute onset
- Occurs over several weeks and is progressive
- Clinical presentation includes aphasia, behavioral and neurophysiological alteration, retrochiasmal visual deficits, hemiparesis, and seizures.

In order to facilitate the recognition of potential PML infection in MS subjects and to minimize the risk of enrolling subjects with undiagnosed or unrecognized PML infection in the clinical study of ponesimod, the following guidance is provided. The proposed algorithm is based on the updated experts' panel recommendation for monitoring subjects who receive treatment with natalizumab [Kappos 2011].

Subjects with known PML infection or evidence of new neurological symptoms or MRI signs within 6 months prior to randomization that are compatible with a diagnosis of PML infection are not be eligible for the study. The proposed algorithm should be applied for all subjects with evidence of new neurological symptoms or MRI signs compatible with PML within 6 months prior to randomization [Figure 6].

Ponesimod / ACT-128800 **Relapsing multiple sclerosis** Protocol AC-058B301, OPTIMUM Version 7

Confidential

5 December 2018, page 104/376

Clinical assessment for potential PML Figure 6

For subjects who have been enrolled in the study and who, under the study treatment, present new neurological symptoms suggestive of pathology other than MS, the investigator should consider PML or another opportunistic infection of the CNS (especially in case of prior exposure to natalizumab or other immunosuppressive agents) and, in case of clinical features indicative of these conditions, the following diagnostic procedures are recommended:

- Perform MRI including T1 sequences with Gd (and additional MRI sequences if needed) and include comparison with the previous MRI images in the interpretation of the MRI results;
- Interrupt study drug until PML or other opportunistic CNS infection has been excluded with confidence;
- Perform lumbar puncture and send cerebrospinal fluid (CSF) for JCV DNA testing by polymerase chain reaction (PCR) with an ultrasensitive assay. The JCV DNA assay should be based on quantitative real-time PCR to maximize sensitivity and specificity for detection, and an assay with a maximum lower limit of quantification of 50 DNA copies per mL should be used.

Detection of JCV DNA in the CSF of a symptomatic subject confirms the diagnosis. However, a negative JCV PCR result should not exclude a possible diagnosis of PML.

In case the CSF is negative but clinical signs and symptoms and/or MRI are still suggestive of PML:

- Consider repeating CSF analysis;
- Consider other opportunistic infections with CNS manifestations;
- Manage the subject on suspicion of PML or other opportunistic CNS infections according to local guidelines.

If,

- There are no suspicious signs of PML or other opportunistic infections on MRI and
- Lumbar puncture, if done, is negative for JC DNA, and
- The neurological signs and symptoms show improvement and are no longer suspicious of PML and can be explained by MS or an alternative, not-infectious etiology,

the suspicion of PML is not supported. Other causes of the atypical neurological signs or symptoms or MRI findings need to be considered. Re-starting of the study drug should be considered if the benefit/risk is still favorable, according to the investigator.

However, if the investigator is still NOT able to rule out PML or another CNS opportunistic infection, the study drug should be permanently discontinued, the case should be reported

to the sponsor as an SAE and the subject should be managed according to the local standard of care.

In case the MRI at scheduled visit shows signs atypical for MS, PML or other opportunistic infection should be considered based on the clinical signs and symptoms, MRI results, previous exposure to natalizumab or immunosuppressants, and laboratory tests including CSF analysis, if indicated. As long as there is suspicion of PML or other opportunistic infection, the study drug should be interrupted and should not be re-introduced until this suspicion has been ruled out.

5.1.13.2.2 General guidance for monitoring of subjects for opportunistic infections other than PML during treatment

Heightened vigilance is required for opportunistic infections, with particular attention to be paid to viral infections. However, investigators and physicians following subjects should also be alert to potential systemic infections caused by fungi and bacteria. In the event of an opportunistic infection, the subject must be referred to an expert in infectious diseases for further examination and treatment. The study drug must be permanently discontinued in case of opportunistic CNS infections. For any other opportunistic infections, the study drug may be interrupted or permanently discontinued at the discretion of the investigator.

It is important to recognize that opportunistic infections caused by the reactivation of human herpes viruses (herpes simplex viruses, varicella-zoster virus, Epstein-Barr virus, cytomegalovirus) may be associated with neurological symptoms primarily. The neurotropic herpes viruses (herpes simplex and varicella-zoster) are frequent human pathogens and their reactivation can cause serious infections of the CNS such as encephalitis and meningitis. The most frequent characteristics of these infections are an acute onset, associated with fever, headache, confusion, personality changes, and disorientation. Any suspicion of these infections must lead to immediate discontinuation of study drug treatment and to early initiation of antiviral treatment [Steiner 2007].

Particular vigilance is required for rare and unusual neurological symptoms, as their recognition is crucial for the early diagnosis of neurotropic herpes viruses infections.

The thorough physical examination and blood tests on the routine visits should be focused on any potential sign of skin, mucosal surfaces, gastrointestinal tract, liver, hematological etc, abnormality and organ dysfunction suggesting a potential opportunistic infection.

Subjects should be advised to be proactive and alert in reporting any unusual neurological symptoms and any signs and symptoms indicative of systemic infections, such as fever, malaise and fatigue [Kappos 2007].

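### The restart rule in Protocol 5.1.13.2 has no CNS exception, so it permits restart after a confirmed and resolved CNS opportunistic infection, for which 5.1.13.2.2 requires a permanent stop

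*Protocol*

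**What the plan says.** Section 5.1.13.2 deals with infections in three moves.

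- For CNS opportunistic infection: "In the event of a suspected opportunistic infection of the CNS, the study drug must be interrupted", with referral to an infectious-disease expert.
- For any other infection, the investigator may interrupt or permanently stop the drug.
- For restart, a single sentence covers study drug interruption in general. The investigator may restart "if the infection is resolved or not confirmed and the benefit/risk balance is considered acceptable for the subject to resume study treatment".

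The section then points onward: "A guidance for screening and monitoring of subjects for opportunistic infection is provided in Sections 5.1.13.2.1 and 5.1.13.2.2".

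Section 5.1.13.2.1 (PML) tells the investigator: "Interrupt study drug until PML or other opportunistic CNS infection has been excluded with confidence". If PML or another CNS opportunistic infection still cannot be ruled out, it says that the drug should be stopped permanently.

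Section 5.1.13.2.2 (opportunistic infections other than PML) is stricter: "The study drug must be permanently discontinued in case of opportunistic CNS infections". It leaves room for judgement only outside the CNS: "For any other opportunistic infections, the study drug may be interrupted or permanently discontinued at the discretion of the investigator". It adds that any suspicion of a neurotropic herpes virus infection must lead to immediate discontinuation.

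**The concern.** The two sections give different answers to one clinical question: after a CNS opportunistic infection has been confirmed and has cleared, may the subject go back on study drug? The general section says that the investigator may decide. The sub-section says that the drug must be stopped for good and names no exception for resolution.

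What is at stake is re-exposure to an immunomodulator after an infection of a kind that the protocol itself describes as serious: it mentions encephalitis and meningitis from herpes reactivation. There is also an administrative consequence. Under section 3, a subject who stops study drug prematurely cannot enter the extension study, while one who is restarted and completes Week 108 can be offered it.

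**Working it through.** No figure is involved, so the check compares the texts.

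**Step 1. Does the restart sentence reach CNS cases?** Three features of section 5.1.13.2 say that it does.

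- It is framed for study drug interruption in general, not for one class of infection.
- The only compulsory interruption in that paragraph is the one for suspected CNS infection.
- Its *not confirmed* limb answers the word *suspected*, which the section uses only for CNS infection.

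**Step 2. Apply the rules to each situation that they must cover.**

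| Situation | Restart sentence, 5.1.13.2 | Sub-sections | Result |
|---|---|---|---|
| CNS infection suspected, then ruled out | may restart | 5.1.13.2.1: restart to be considered if benefit/risk is favourable | agree, apart from the herpes sentence in 5.1.13.2.2 |
| CNS infection not confirmed, not yet excluded | may restart if not confirmed | 5.1.13.2.1: guidance on how suspicion is excluded | consistent if read as guidance under the general rule |
| CNS infection confirmed, then resolved | may restart | 5.1.13.2.2: must stop permanently | **conflict** |
| CNS infection confirmed, unresolved | no route to restart | 5.1.13.2.2: must stop permanently | agree |
| Other infection | investigator's discretion | 5.1.13.2.2: investigator's discretion | agree |

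Count: 1 conflict + 4 without conflict = 5 situations. This shows the scope of the problem and is not a frequency.

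**Step 3. Does other text settle the conflict?**

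- The list at the start of 5.1.13.2 of findings that compel a permanent stop contains only neutrophil, platelet and lymphocyte counts. CNS infection is not on it.
- The pointer to the two sub-sections describes them as guidance on screening and monitoring. It does not make restart subject to them.
- Section 5.1.9 does not end the interruption when infection is confirmed: "The duration of an interruption is determined by the investigator and is not limited in time", and "At maximum, it will last until the investigator deems the subject necessary to require another MS treatment". It does refer to 5.1.13 for the study-specific criteria, which leads back to the same two texts.
- Section 5.1.13.5 (liver) has a similar discretionary restart, but adds that restart is not allowed where Table 6 calls for a permanent stop. Section 5.1.13.2 has no such line.

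**The case against.** The strongest reply is that the texts can be reconciled. A permission and a prohibition can both be obeyed: an investigator who stops the drug permanently under 5.1.13.2.2 breaches nothing in 5.1.13.2. The CNS sentence in 5.1.13.2 concerns a suspected infection, whereas 5.1.13.2.2 concerns an actual one. On confirmation the subject would therefore move to permanent discontinuation, a branch that 5.1.13.2 also covers by requiring monitoring until the infection has fully resolved. On that reading *not confirmed* belongs to the CNS case, *resolved* belongs to other infections, and the specific rule governs the general one.

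This is a sensible account of the likely intent, and it shows that sites can comply with both sections. But no words allocate the two limbs in that way or give the sub-section precedence. An investigator who relies on the restart sentence alone would be acting within its terms while doing what 5.1.13.2.2 forbids.

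A reader might also infer that the *not confirmed* limb sets too low a bar, because 5.1.13.2.1 asks for exclusion with confidence and warns that a negative JC virus PCR does not exclude PML. The protocol does not support counting this as a second error. That text is guidance on how suspicion is to be excluded, and it can be read as spelling out what *not confirmed* requires.

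**Conclusion.** The point holds in a narrow form. As worded, section 5.1.13.2 permits discretionary restart after a confirmed and resolved CNS opportunistic infection, and section 5.1.13.2.2 requires permanent discontinuation. It rests on reading the restart sentence as covering every interruption, which is what its words say.

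A reader might infer that the mandatory rule is equally contradicted for PML. That goes too far: the mandatory sentence stands under a heading for infections other than PML, and the permanent-stop text in the PML sub-section is a recommendation for cases that cannot be ruled out. Nor would it be right to infer that subjects stay on drug during an active CNS infection, since drug stops on suspicion under every reading.

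Severity is low. The events are assumed to be rare; the protocol gives no rate. Subjects who stop early are still followed to Week 108 in the post-treatment observation period, provided they do not withdraw consent. Alpha, power and sample size are untouched. The correction is still worth making, because it protects subjects and costs little.

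**What to change.** Amend the restart sentence in 5.1.13.2 so that *resolved* applies only to infections other than CNS opportunistic infections, and add an exclusion modelled on the liver section, for example:

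> Re-initiation is not permitted after a confirmed CNS opportunistic infection, even if resolved (Section 5.1.13.2.2). After a suspected one, study drug may be re-initiated only once it has been ruled out as described in Section 5.1.13.2.1, and subject to the neurotropic herpes virus rule in Section 5.1.13.2.2.

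Two points need the sponsor's attention when adopting this. The first sentence of the example would also cover confirmed PML, so the sponsor should confirm that this is intended; the recommendation in 5.1.13.2.1 for cases that cannot be ruled out keeps its present strength. The herpes sentence stays as it is and takes priority where it applies, but it does not say whether the discontinuation on suspicion is permanent, and the sponsor may wish to state that.

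The cost is a short wording change in one section, made through a protocol amendment, and a letter to sites. Data collection and analysis do not change.
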